3.5. OTHER EFFICACY ENDPOINTS

The following other efficacy endpoints will be summarized to assess the treatment effect using the FAS.

The endpoints related to the number of days on actual PS a week will be derived using the selected valid 7-day period used for the primary endpoint. Additionally to summary statistics, these endpoints will be analyzed with the same methodology as for the primary analysis of the confirmatory binary endpoints.

Reduction in days on actual $PS \ge 2$ days per week from baseline to Week 24

The number and percent of patients who have a reduction in days on $PS \ge 2$ days per week from baseline to Week 24 will be presented for each glepaglutide treatment group and placebo

Reduction in days on actual PS \geq 3 days per week from baseline to Week 24

The number and percent of patients who have a decrease in days on $PS \ge 3$ days per weekfrom baseline to Week 24 will be presented for each glepaglutide treatment group and25 August 2022ConfidentialPage 25 of 65

placebo.

Change in duration of actual PS infusions per week from baseline

The change will be presented as descriptive statistics at Weeks 1, 2, 4, 8, 12, 16, 20, and 24.

Concentration trough levels of glepaglutide and metabolites

Concentration trough levels of glepaglutide and metabolites will be summarized descriptively. The number of non-missing observations, mean, SD, median, minimum, and maximum values will be presented by visit.

Change in plasma citrulline levels from baseline to Week 24

The change in plasma citrulline levels from baseline to Week 24 will be presented descriptively and include the number of non-missing observations, mean, SD, median, minimum, and maximum values.

Change in weekly need for parenteral micronutrients (sodium, potassium, magnesium, and calcium) from baseline to Week 24

The change in weekly need for parenteral micronutrients from baseline to Week 24 will be summarized using number of non-missing observations, mean, SD, median, minimum, and maximum values for sodium, potassium, magnesium, and calcium.

For a given visit the parental micronutrients content will be derived from the eDiary values recorded during in valid 7-day period used for deriving the actual weekly PS volume.

Actual PS intake of micronutrients will be used for the analysis involving PS content. Each of the 4 micronutrients will be summarized separately (for sodium, potassium, magnesium, and calcium).

Change in PROs (SBS-I and EQ-5D-5L) from baseline to Week 24

The change in patient-reported outcome scores (SBS-I and EQ-5D-5L) from baseline to Week 24 will be presented descriptively and include the number of non-missing observations, mean, SD, median, minimum, and maximum values.

For SBS-I, the average ordinal change from baseline to Week 24 for each question will be calculated for all patients combined and by each SBS Anatomical Group (see Section 3.1 for the SBS anatomical subgroups definition). Differences in the average change between each glepaglutide treatment regimen compared to placebo will be tested using a t-test. The sum of scores for each question will be calculated and the difference in change from baseline to Week 24 between each glepaglutide treatment regimen compared to placebo will be assessed using a t-test.

For EQ-5D-5L, results will be presented in three ways.

25 August 2022

- 1. Presenting results from the EQ-5D-5L descriptive system as a health profile at baseline and Week 24: The frequencies and percentages of each level of problem (No problems, Slight problems, Moderate problems, Severe problems, and Extreme problems/unable to do) will be presented at baseline and at Week 24 for each health dimension (Mobility, Self-care, Usual Activities, Pain/Discomfort, and Anxiety/Depression) by treatment group. A further frequency/percentage summary by demographic subgroup (e.g., age group, sex) and/or by SBS Anatomical Group may be presented if applicable.
- Presenting results of the EQ VAS as a measure of overall self-rated health status: The EQ VAS will be presented descriptively for n, mean, standard deviation, median, minimum value, maximum value, 25th percentile, and 75th percentile by treatment group at baseline and at Week 24.
- 3. Presenting results from the EQ-5D-5L index value: The index value will be presented descriptively using n, mean, standard deviation, median, minimum value, maximum value, 25th percentile, and 75th percentile by treatment group at baseline and at Week 24. Differences in the mean values between each glepaglutide treatment regimen compared to placebo will be tested using a t-test. Subgroup tables by demographic and/or baseline characteristics (e.g., age group, sex, smoking status, etc.) and/or by SBS Anatomical Group may be presented if applicable.

Change in bowel movements or stoma bag emptying from baseline to Week 24

The number of bowel movements recorded in the eDiary during the 48-hour period prior to baseline and Week 24, and the change from baseline to Week 24 will be presented descriptively. The number of stoma bag emptyings recorded in the eDiary during the 48-hour period prior to baseline and Week 24 will be summarized in a similar manner, for the subset of patients in the FAS who have a stoma.

Measurements of hydrational status

To evaluate the trends on hydration status the urine volume (mL) and the oral fluid intake (mL) recorded by the patients in the eDiary during 48-hour periods prior to the nominal visits will be presented graphically together with the actual weekly PS volume (L/Week) as follows:

- The individual trajectories of 48-hour urine volume (mL), 48-hour oral fluid intake (mL) and weekly PS volume (L) recorded in the patients in the eDiary will be plotted by actual times (start of 48-hour period or visit). Profiles will be gathered in different panels by SBS anatomical classification and treatment group.
- Mean plots of urine volume (mL by 48-hours), oral fluid intake (mL by 48-hours) and actual weekly PS volume (L/Week). Plots by nominal visit and treatment group
 - y1-axis L/Week (for actual weekly PS volume)
 - y2-axis mL/48-hours (for urine volume and oral fluid intake)

25 August 2022

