7.5 Patient Withdrawal or Discontinuation from Trial Treatment

The patient is free to withdraw consent at any time during the trial. The patient's request to withdraw from the trial must always be respected.

All data collected from a withdrawn patient prior to withdrawal and during the final visit will be included in the analyses of the trial data. Although a patient is not obliged to give his/her reason(s) for withdrawing consent, the Investigator must make a reasonable effort to ascertain the reason(s), while fully respecting the patient's rights. An end of trial form must be completed and final drug accountability done even when patients are not able to come for a trial visit.

Only patients who withdraw their consent will be considered as withdrawn from the trial.

For patients who permanently discontinue from trial treatment (i.e. there is no plan to resume trial treatment or to enter the Extension Trial) every effort must be made to ensure patients attend and complete all scheduled visit procedures to the extent possible. Patients should stay in the trial regardless of compliance with trial drug, assessments, or visit schedule.

The investigators should make a special effort to ensure that all patients complete the assessment of actual PS volume in Week 24 (primary endpoint).

Patients who permanently discontinue from trial treatment and the trial (without withdrawal of consent) should be asked to come to the site for an EOT visit during which all general, safety, and laboratory assessments should be performed as detailed in the schedule of assessments. During this visit, the Investigator should also discuss further treatment options for SBS with the patient. Note: if a patient is discontinued during a trial visit, efforts should be made to complete all trial-related assessments for the EOT Visit. If not participating in the Extension Trial, the patient should attend the FU/Final visit.

A patient must be discontinued from trial treatment if:

1. Any safety concerns or AEs that in the opinion of the Investigator might place the patient at unacceptable risk, including any deterioration of a patient's health state, especially in terms of the frequency and volume of total PS.
2. Any malignancy.
3. Increased liver values, defined as:
 - a. ALT or AST >3 times baseline value lasting more than 2 weeks*, or
 - b. ALT or AST >5 × ULN and total bilirubin >2 x ULN*, or
 - c. ALT or AST >5 × ULN and INR >1.5*, or

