3. ENDPOINTS

3.1. PRIMARY EFFICACY ENDPOINT

The primary efficacy endpoint is the change in actual weekly PS volume from baseline to Week 24.

Baseline actual weekly PS volume is defined as the actual PS volume derived from a valid 7-day period prior to Visit 1 (Day 1), i.e. during the stabilization phase. The actual weekly PS volume at Weeks 1, 2, 4, 8, 12, 16, 20, and 24 will be derived as the actual weekly PS volume received during the valid 7-day period prior to the visit. The source for the derivation will be the PS volumes recorded by the patients in the eDiary; for details on the derivation of actual weekly PS volume see Appendix A. Supportive analyses will be performed to explore the robustness of the primary analysis with regard to the algorithm for deriving the primary endpoint, see 3.1.4.

Following the treatment policy strategy, for patients who prematurely discontinue treatment but complete the trial providing eDiary information up-to Week 24, the actual weekly PS volume derived at Week 24 after treatment discontinuation will be included in the primary analysis of the primary efficacy endpoint. For patients who prematurely discontinue treatment and did not complete the trial, having an end of treatment visit (Visit 10) prior to Week 24 - 14 days (169-14 days), the derived actual weekly PS volume at the end of treatment visit will not be carried forward to represent Week 24. Instead 1) the value at Week 24 will be set to missing and imputed with the multiple imputation method described below for the primary analysis of the primary endpoint and 2) the derived actual weekly PS volume at the end of treatment visit will be re-allocated to a previous visit and used in the MMRM model. If, when re-allocating the end of treatment visit there is already a visit in the same time window, then the value of the scheduled visit will be used in the analysis, not the re-allocated end of treatment value.

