7.3. CLINICAL LABORATORY EVALUATIONS

Clinical laboratory parameters include:

Hematology:

Hemoglobin, Hematocrit, Red blood cell (RBC) count, White blood cell (WBC) count with differential (including absolute value and % value for neutrophils, lymphocytes, monocytes, basophils, and eosinophils), Platelet count, and International normalized ratio (INR)

Biochemistry:

Sodium, Potassium, Chloride, Bicarbonate, Blood urea nitrogen, Creatinine, Estimated creatinine clearance, Glucose, Calcium, Phosphorous, Magnesium, Alkaline Phosphatase, Alanine Aminotransferase (ALT), Aspartate Aminotransferase (AST), Gamma-glutamyl transferase (GGT), Lactic dehydrogenase, Conjugated bilirubin, Total bilirubin, Total protein, Triglycerides, Cholesterol, Albumin, Amylase, Uric acid, Zinc, and C-reactive protein (CRP)

Urine:

Blood, Glucose, Leukocytes, pH, Osmolality, Protein, Sodium, and Potassium

Confidential

Hematology, biochemistry, and pregnancy laboratory tests performed by a central laboratory will be included in ADLB dataset.

Due to the COVID-19 public health emergency, some of the trial participants were not able to come to the investigational site for all protocol-specified visits. Instead, the visits could be conducted as phone visits, if considered safe by the investigator. The investigator could also refer the patient to a local laboratory, if deemed necessary.

In general (independent of the COVID-19 pandemic), blood samples for analysis at a local laboratory can be drawn at the investigator's discretion during the trials; these values will be included in narratives for SAEs and AESIs as appropriate.

Descriptive statistics of the laboratory parameters will be presented by treatment group for all nominal trial visits at which they were collected. The change from baseline in hematology and biochemistry values will also be summarized by treatment group. Summary tables will also include the end of trial value defined as is the last available value in the trial and also the highest and lowest post-baseline values including values from unscheduled visits.Box plots of actual values will be produced for all hematology and biochemistry parameters. For laboratory parameters that are log-transformed the geometric mean will be presented in the box plot.

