7.7.2. Immunogenicity Statistical Methodology

All analyses will be done for all four ADA assessments (ADA, NAb, M2 reactivity and GLP-2 cross-reactivity), unless otherwise specified.

The overall anti-glepaglutide antibody incidence (sum of treatment boosted and treatment induced) will be tabulated by treatment group and visit, and overall (incidence of patients ADA positive any time during trial). Similar tables will be made separately for treatment boosted and treatment induced ADAs, if both types are observed. In addition, the ADA incidences by visit will be presented graphically.

For all treatment induced ADA positive patients, the titer levels will be summarized by treatment group and visit using descriptive statistics including median, geometric mean, geometric CV%, inter-quartile range, minimum, maximum, and number of observations (positive samples only).

For all treatment boosted ADA positive patients (if applicable), the titer levels and fold increases from baseline of titers will be summarized by treatment group and visit using descriptive statistics including median, geometric mean, geometric CV%, inter-quartile range, minimum, maximum, and number of observations (positive samples only).

Spaghetti plots of individual trajectories over time of ADA titers (and fold increases of ADA titers, if applicable) will be presented for each treatment group. Plots of the geometric mean ADA titers by visit and treatment group will be presented.

All immunogenicity data will be listed, including corresponding PK concentrations.

Investigating immunogenicity impact on efficacy and safety

To assess the impact of ADA on efficacy and safety, the results for each of the ADA assessments (ADA, NAb, M2 reactivity and GLP-2 cross-reactivity) will be categorized into three levels (negative, low titer positive, and high titer positive).

The ADA results will be grouped as either 1) or 2):

25 August 2022

- (1) ADA status/titer, if more than 5 patients have positive outcome in the assessment:
 - a. Level 1: ADA negative
 - b. Level 2: ADA low titer positive (titers \leq median titer at Week 24)
 - c. Level 3: ADA high titer positive (titers > median titer at Week 24)
- (2) ADA status/titer, if 5 patients or less have positive outcome in the assessment:
 - d. Level 1: ADA negative
 - e. Level 2: ADA positive

The median titer at Week 24 will be calculated for the ADA positive samples only.

Immunogenicity association with PK

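### An early end-of-treatment visit is barred from standing for Week 24 for PS volume only, and the PK trough definition does not require the patient to be on drug

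*SAP*

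**What the plan says.** **The rule for PS volume.** SAP 3.1 deals with patients who stop treatment and do not complete the trial, "having an end of treatment visit (Visit 10) prior to Week 24 - 14 days". For them, "the derived actual weekly PS volume at the end of treatment visit will not be carried forward to represent Week 24". The Week 24 value is set to missing and imputed. The early value is moved to a previous visit, unless a scheduled value already occupies that time window. PS volume observed off drug at a true Week 24 is kept, under the treatment policy strategy.

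**The samples.** Protocol 7.5 says that patients who leave both treatment and trial without withdrawing consent "should be asked to come to the site for an EOT visit during which all general, safety, and laboratory assessments should be performed". Protocol 10.4.10 gives Visit 10, End of Treatment and Week 24 as one visit, with citrulline, PK, ADA and safety laboratory samples. Footnote 11 of the schedule of assessments also asks for an ADA sample at EOT after treatment discontinuation.

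**The outputs.**
- Citrulline (SAP 3.5): "The change in plasma citrulline levels from baseline to Week 24 will be presented descriptively".
- PK (SAP 3.5): "Concentration trough levels of glepaglutide and metabolites will be summarized descriptively", by visit.
- Laboratory (SAP 7.3): descriptive statistics "will be presented by treatment group for all nominal trial visits at which they were collected", plus an end-of-trial row holding the last available value.
- ADA (SAP 7.7.2): low and high titer are split at the Week 24 median, and "The median titer at Week 24 will be calculated for the ADA positive samples only". Selected adverse events are tabulated by Week 24 titer category.

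**Trough.** The only definition is in SAP 7.7.2, for the ADA-PK plots: a sample over 60 hours after the last glepaglutide dose. It sets no upper limit and does not require that dosing is continuing.

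**The concern.** SAP 3.1 recognises that the Visit 10 label does not guarantee 24 weeks of follow-up, and corrects for this in one variable. The blood samples from that visit have the same labelling problem and no correction. If a programmer follows the nominal visit, a sample from a patient who left months early becomes a Week 24 value. It then enters the citrulline change, the by-visit laboratory and PK summaries, the median titer that defines the ADA categories, and the Week 24 category of that patient.

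The trough issue is separate and does not depend on early visits. Patients who stop drug but stay in the trial are asked to keep attending (Protocol 7.5), pauses may total 4 weeks (Protocol 7.6), and PK is drawn at every site visit of the Treatment Phase (Protocol 11.3.6.7). Samples from these patients meet the trough definition however long ago the last dose was. They can lower the summarised trough. In the ADA-PK plots, an antibody-positive patient who has stopped drug can look like one whose antibodies removed the drug.

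**Working it through.** The plan states no figure on this point, so there is none to reproduce. The check sets the texts side by side and adds two illustrations.

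**1. Timing.** The SAP 3.1 cut-off is 169 − 14 = Day 155. The protocol window for Visit 10 is 169 ± 7, or Days 162 to 176. An EOT visit before Day 155 is therefore outside the Visit 10 window by at least 162 − 154 = 8 days, yet it keeps the Visit 10 label.

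**2. Does another rule catch these samples?**
- SAP 5.1 keeps unscheduled and repeat assessments out of summary tables. It does not name an early EOT visit.
- SAP 5.2 defines baseline only.
- SAP 5.3 sets period rules for PS volume only.
- SAP 3.5, 3.7, 7.3 and 7.7 contain no analysis window or re-allocation rule for citrulline, PK, ADA or laboratory values.

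The allocation is therefore unspecified, and the nominal label points to Week 24.

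**3. Possible effect on a Week 24 mean change (illustration).** Assume an arm of 36 with all values present, an assumed share d of early EOT samples counted as Week 24 (k patients, 36 × d rounded), and early values carrying a fraction f of the full Week 24 change. The mean change that remains is 1 − (k/36)(1 − f).

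| d (assumed) | k | f = 0 | f = 0.5 |
|---|---|---|---|
| 5% | 2 | 1 − 2/36 = 94% | 97% |
| 10% | 4 | 1 − 4/36 = 89% | 94% |
| 15% | 5 | 1 − 5/36 = 86% | 93% |

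Neither d nor f is in the documents. SAP 5.3.1 says only that few patients on active treatment are expected to discontinue.

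**4. Possible effect on a mean trough (illustration).** This concerns a different group: patients off drug or in a pause who still attend. If one such sample among 36 holds a fraction g of the on-drug mean, the arm mean is multiplied by 1 − (1 − g)/36. At the extreme g = 0, each such sample lowers the mean by 1/36 = 2.8%. Neither the number of such samples nor g is known.

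**The case against.** The strongest reply is that little depends on these outputs. Citrulline and trough summaries are descriptive, PK endpoints are exploratory, and the ADA associations are plots and summaries. Few discontinuations are expected, medians are reported beside means, and a median titer cut is insensitive to a few values. SAP 7.3 already has a last-available row, and SAP 7.7.2 also plots all concentrations regardless of timing and lists immunogenicity data with the matching PK. All of this stands, and it sets the severity.

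A reader might also draw stronger conclusions that the documents do not support:

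- *That the SAP assigns early samples to Week 24.* It is silent. The text supports only that they may be counted there.
- *That off-drug values in general should be kept out of Week 24.* The SAP 3.1 rule concerns early visits. Off-drug PS volume at a true Week 24 is kept deliberately, and off-drug citrulline at a true Week 24 fits that approach. Only the trough raises a separate off-drug question.
- *That bone-marker results are distorted.* The SAP calls bone markers exploratory and specifies no Week 24 output for them, so there is no defined result to distort.
- *That Week 28 samples contaminate the troughs.* The plots stop at Week 24 and the summary is by visit.
- *That the mean trough is understated by about 6 to 11%.* This takes 2/36 to 4/36, treats early leavers as if they were off-drug patients still attending, and sets their levels near zero. The two groups differ, and Protocol 4.2 describes protracted PK from a subcutaneous depot.

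**Conclusion.** The point holds in two limited parts.

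1. The protection against an early Visit 10 standing for Week 24 covers actual weekly PS volume only. Citrulline, PK, ADA and safety laboratory samples from that visit may be summarised as Week 24, including in the median titer and the titer categories.
2. The trough definition and the by-visit trough summary, followed as written, admit samples taken after permanent discontinuation or within a pause. Any resulting error in the mean trough is expected to be downward, and the ADA-PK plots can then suggest a loss of exposure that is only the end of dosing.

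The size cannot be stated because the documents give no discontinuation rate. The figures under the working rest on assumed shares and on an assumed content of the affected samples. No confirmatory test, significance level or power figure is involved. Severity is low, but the allocation should be fixed in writing before unblinding and not left to programming.

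**What to change.** **(1) Week 24 allocation.** In SAP 5.2 or 5.3, state that an EOT (Visit 10) sample taken before Day 155 is not used as Week 24 for citrulline, PK, ADA titer, the median titer, the titer category or by-visit laboratory summaries. List it, and keep it in the end-of-trial (last available) row where one exists. Re-allocate it to an earlier visit only if that assessment is scheduled there and has no value. Unconditional re-allocation would not work. The Week 4 window is Days 24 to 34 and the Week 8 window Days 52 to 62, so a Day 43 sample falls in neither. Between Visits 1 and 10, citrulline is scheduled only at Visit 5, and ADA is not scheduled at Weeks 16 or 20.

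**(2) Trough.** Add an on-treatment condition to one trough definition used in both SAP 3.5 and 7.7.2. Exclude samples taken after permanent discontinuation or within a treatment pause from the trough summary and trough plots, and list them separately. They remain in the plots of all concentrations. An on-treatment condition is simpler than a single upper limit in hours, because active doses are 3 to 4 days apart in one arm (72 to 96 hours) and 7 days apart in the other (168 hours). Off-drug citrulline at a true Week 24 stays in.

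**Cost.** A few sentences, a dataset flag, and a few fewer values in the Week 24 and trough tables. Early leavers would have no Week 24 titer category, so the adverse-event table by category should show them in a row of their own. No visit, sample or clinical rule changes.
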